4.3.2 Exclusion Criteria

1. Bleeding site in the neck, head, or brain.
2. Subject has co-morbidity with survival prognosis of less than 30 days, in the opinion of the treating physician
3. In the investigator's opinion, participation in the study may not be in the subject's best interest.
4. Pregnant woman, person under guardianship or curatorship, persons under judicial protection, and persons who do not write or speak French (applicable in France only).

Refer to the EmboCube Embolization Gelatin IFU for a complete list of device contraindications.

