3.2 Design

Multicenter, observational, post-market clinical follow-up study in subjects treated with EmboCube.

This study does not involve submitting subjects to any procedures additional to those performed under normal conditions of use of the device.

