5 SCREENING AND ENROLLMENT

5.1 Screening

All consecutive patients who meet the eligibility criteria should be considered for enrollment in the study. Sites should maintain a cumulative log of all screened and enrolled subjects. The Investigator or designee should determine potential eligibility according to Section 4.3. Patients who meet all criteria should be provided with further information on the study in accordance with the procedures in Section 5.2.

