8.4 Overall Assessment of Risk-Benefits

This is an observational registry using commercially available devices and there are no new risks or benefits to the individual subject associated with study participation.

The additional information obtained on the safety and effectiveness profile of the device may benefit physician understanding of the use of embolics and may support the development of new devices in general. Therefore, Sponsor's assessment is that the potential benefits justify the study.

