9.4 Sample Size

The sample size of 100 subjects is based on a one-sample non-inferiority analysis of Clinical Success based on the parameters listed below and a 15% loss-to-follow-up:

- Reference Clinical Success rate (p_0): 92%

- Treatment rate (p): 90%
- Non-inferiority margin: 10%
- α : 0.05
- Power: 80%

The reference Clinical Success rate is based on historical clinical literature data for benchmark gelatin embolic devices.

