5.3.2 EXCLUSION CRITERIA

French Study Sites

1. Site of bleeding is in the neck, head, or brain
2. Subject has a co-morbidity with survival prognosis < 30 days, in the opinion of the treating physician
3. In the investigator's opinion, participation in the study may not be in the subject's best interest
4. Pregnant woman, person under guardianship or curatorship, person under judicial protection, and/or person who does not write or speak French (applicable in France only)

Australian Study Sites

1. Subject's vascular anatomy precludes correct catheter placement
2. Subject's feeding arteries are too small to accept selected EmboCube
3. Bleeding site in the neck, head, or brain
4. Presence or suspicion of vasospasm
5. High-flow arteriovenous shunts with a diameter greater than the selected EmboCube
6. Use in the pulmonary vasculature
7. Use in pre-operative portal vein embolization
8. Subject has severe atherosclerosis
9. Subject has known allergy to gelatin of porcine origin
10. Subject has a co-morbidity with survival prognosis of < 30 days in the opinion of the treating physician
11. In the investigator's opinion, participation in the study may not be in the subject's best interest

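### Two opinion-based exclusions have no time anchor, so for treated patients not yet consented eligibility can be decided after the 24-hour outcomes are known

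*Protocol*

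**What the plan says.** Protocol 4.3.2 has two exclusions that rest on opinion. Item 2 reads "Subject has co-morbidity with survival prognosis of less than 30 days, in the opinion of the treating physician". Item 3 leaves it to the investigator whether "participation in the study may not be in the subject's best interest". SAP 5.3.2 repeats both, the first as "Subject has a co-morbidity with survival prognosis < 30 days, in the opinion of the treating physician" in the French list. They are items 2 and 3 in the French list and items 10 and 11 in the Australian list. No version gives a time point or an information cut-off.

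On sequence, Protocol 5.1 says "The Investigator or designee should determine potential eligibility according to Section 4.3", after which eligible patients receive study information. That places the check before the approach for consent, but not before the procedure. Protocol 5.2 expects that consent before the procedure will often be impossible. It allows consent until discharge or day 7, whichever comes first, and bars data collection before consent. Protocol 5.3 sets enrollment at consent and keeps enrolled, treated subjects in follow-up if they are later found ineligible. Protocol 9 and SAP 6 define ITT as all enrolled subjects. Both primary endpoints close at 24 hours (Protocol 4.1).

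**The concern.** For a patient approached after the first 24 hours, the person judging 30-day prognosis or best interest may already know whether bleeding recurred, whether a re-intervention was needed, or whether a serious device effect occurred. The treating physician who gives the prognosis opinion may also be the operator. If that knowledge influences the judgement, inclusion depends on the outcome being estimated. Clinical success would then be biased upward and the frequency of serious device effects downward.

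This matters more in a single-arm study, where Protocol 10.18 relies on consecutive enrollment to limit bias. Under Protocol 5.1, consecutive enrollment covers patients who meet the eligibility criteria, so an exclusion made with knowledge of the outcome would still comply with it.

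**Working it through.** **1. Can the route occur under the text as written?**

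| Step | Source | What it settles |
|---|---|---|
| Opinion exclusions carry no time point | Protocol 4.3.2; SAP 5.3.2 | Judgement after the procedure is not barred |
| Eligibility precedes study information | Protocol 5.1 | Tied to the consent approach, not to embolization |
| Consent up to discharge or day 7 | Protocol 5.2 | Can fall after the 24-hour endpoints |
| Enrollment is at consent; ITT is all enrolled | Protocol 5.3 and 9; SAP 6 | A patient ruled out before consent is never in ITT |
| Enrolled subjects found ineligible are retained | Protocol 5.3 | Closes the route in ITT for anyone already consented |
| Eligibility deviations are major | Protocol 10.15; SAP 8.1.4 | Those retained subjects leave only the supportive per-protocol set |

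The route is open for one group only: treated patients not yet consented. Protocol 5.1 requires a screening log, but does not require it to record which criterion failed or when.

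**2. The plan's own figure.** Protocol 9.4 states "The sample size of 100 subjects is based on a one-sample non-inferiority analysis of Clinical Success", with "Reference Clinical Success rate (p_0): 92"%, expected rate 90%, margin 10%, alpha 0.05, power 80% and 15% loss to follow-up. The implied boundary is 92% − 10% = 82%. With the variance taken at p and one-sided alpha:

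n = p(1−p) × [(z(0.95) + z(0.80)) / (p − 0.82)]² = 0.09 × (2.486 / 0.08)² = 86.9, so 87.

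For loss to follow-up, 86.94 × 1.15 = 99.98, which gives the stated 100; 87 / 0.85 gives 103. The stated figure is reproduced. Sidedness is not stated; one-sided is the reading that fits.

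**3. Effect of selective removal.** Let p be the true success rate among treated patients and f the share of failures ruled out before consent, with no successes removed. The enrolled rate is

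p / [p + (1−p)(1−f)].

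The documents give no value for f, so the values below are assumptions.

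| f | True 90% | True 82% |
|---|---|---|
| 0 | 90.0% | 82.0% |
| 10% | 90.9% | 83.5% |
| 25% | 92.3% | 85.9% |
| 50% (extreme) | 94.7% | 90.1% |

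Example for f = 25% and p = 90%: 0.90 / (0.90 + 0.10 × 0.75) = 0.90 / 0.975 = 92.3%.

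Only late-consented patients are exposed. If half are consented late and a quarter of the failures among them are ruled out, f = 0.5 × 0.25 = 12.5%, and 90% becomes 91.1% while 82% becomes 83.9%.

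**4. Exact intervals when true success is 82 of 100 treated.** SAP 8.1 plans Clopper-Pearson 95% limits.

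| Failures removed | Reported | Lower limit |
|---|---|---|
| 0 of 18 | 82/100 = 82.0% | 73.1% |
| 6 of 18 | 82/94 = 87.2% | 78.8% |
| 8 of 18 | 82/92 = 89.1% | 80.9% |
| 9 of 18 | 82/91 = 90.1% | 82.1% |

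In this table the lower limit exceeds 82% only when half of all failures are removed.

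**5. After the fix.** If the criteria may use only pre-embolization information, f for this route is 0, the enrolled rate equals the treated rate, and N is unchanged.

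**The case against.** The strongest reply is that the plan already limits this. Subjects found ineligible after enrollment stay in, so nobody already consented can be removed from the primary analysis. A screening log is required and consecutive enrollment is requested. The prognosis criterion needs a co-morbidity, so a failed embolization or a re-bleed alone does not meet it. All of this stands, and it confines the point to treated, not-yet-consented patients and mainly to the best-interest criterion. It does not close the gap: the retention rule does not reach those patients, and the log need not show why or when they were ruled out.

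It can also be said that the route exists only because consent may be late, and that a site could simply not approach a patient. That is true, and a time anchor does not prevent it. But early consent is often infeasible by the Protocol's own account, whereas an information cut-off can apply however late consent comes.

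Two stronger readings are tempting. A reader might infer that the best-interest exclusion has no basis and should go, because Protocol 3.2 says "This study does not involve submitting subjects to any procedures additional to those performed under normal conditions of use of the device" and Protocol 8.4 says "there are no new risks or benefits to the individual subject associated with study participation". The documents do not support that. The SAP synopsis lists the device as investigational in Australia, where the same criterion applies, so the commercial-device premise cannot simply be carried over. A time anchor deals with the bias without removing the discretion.

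A reader might also infer that a device at 82% could pass a non-inferiority test. Protocol 9 calls the analysis primarily descriptive, and Protocol 9.2 and SAP 8.2 present clinical success as a frequency and percentage. No test against 82% is specified, so comparisons with that value are illustrative.

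**Conclusion.** The point holds within limits. As written, the prognosis and best-interest exclusions can be judged with the 24-hour outcomes in hand for treated patients who have not consented, and those ruled out leave no outcome data. Nothing in the documents shows that this will happen or how often.

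The size rests on the assumed f and on removals falling only on failures. At f of 10% to 25%, the reported rate rises by about 1 to 2 percentage points from a true 90%, and by about 1.5 to 4 points from a true 82%. The direction is the same for serious device effects, but the documents give no rate from which to size that. This is a cheap improvement; it is not a flaw that invalidates the study.

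**What to change.** In Protocol 4.3 and SAP 5.3, state that the prognosis and best-interest exclusions are judged only on information available before the start of embolization, and that events during or after the procedure may not be used. Name the criteria and do not cite item numbers: in the SAP's Australian list, items 1 to 3 are catheter placement, feeding-artery size and bleeding site. Keep the best-interest criterion.

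Add two fields to the existing screening log for each EmboCube-treated patient not enrolled: the criterion that failed, and whether the decision was made before or after the procedure. Report these counts by criterion beside the primary endpoints.

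The cost is one sentence in each document, two log columns and one small table. Sites lose some discretion, and the reported success rate may be slightly lower because a few sicker patients stay in. The sample size is unaffected.

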5 SCREENING AND ENROLLMENT

5.1 Screening

All consecutive patients who meet the eligibility criteria should be considered for enrollment in the study. Sites should maintain a cumulative log of all screened and enrolled subjects. The Investigator or designee should determine potential eligibility according to Section 4.3. Patients who meet all criteria should be provided with further information on the study in accordance with the procedures in Section 5.2.

5.2 Informed Consent

As bleeding or hemorrhaging requiring embolization occurs in unplanned and/or emergency circumstances, it is anticipated that, in many cases, it will not be possible to obtain written informed consent prior to procedure. This is an observational study and study consent is required for collection and use of patient data, including telephone contact for safety review if required. There are no additional procedures or tests required in addition to routine standard of care. Written informed consent (or non-opposition consent, if applicable), to collect and use data will be collected with the Ethics Committee (EC)/Institutional Review Board (IRB) approved consent form prior to procedure, if feasible. If written consent cannot be collected before the procedure, it should be collected as soon as possible after procedure but no later than time of subject discharge or 7 days post-procedure, whichever occurs first. No data collection can occur until subject has provided written informed consent.

The subject shall be given adequate time to read the Informed Consent form and have the data collection and data transmission procedures explained prior to signing the Informed Consent form. All subjects providing informed consent for data collection are to receive copies of their signed informed consent documentation.

The Sponsor will inform the investigators whenever information becomes available that may be relevant to the subject's confirmed participation in the study. The investigator or designee should inform the subject in a timely manner.

The Sponsor will revise the Informed Consent form whenever new information becomes available that may be relevant to the subject's confirmed participation in the study. The revised information will be sent to the investigator for approval by the EC/IRB. After approval by the EC/IRB, a copy of this information must be provided to the participating subjects, and the informed consent process as described above needs to be repeated.

5.3 Enrollment

All subjects who provide written informed consent for the study, meet all eligibility criteria, and are treated with EmboCube Embolization Gelatin will be considered enrolled in the study.

Subjects who are consented prior to procedure but subsequently do not receive EmboCube Embolization Gelatin will be considered screen failures. These subjects will be entered on the screening log, but no data will be collected on screen failures.

Subjects who are enrolled and treated, but who are later discovered to not meet all the eligibility criteria will remain in the study for follow-up and a Protocol Deviation form will be completed.

Point of enrollment is the time of informed consent.

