9 STATISTICAL ANALYSIS

The analysis of the data from this study will be primarily descriptive. Continuous endpoints will be summarized by N, mean, standard deviation, median, minimum, and maximum. Categorical or binary endpoints will be summarized by N and percentage with confidence intervals as appropriate. Kaplan Meier plots will be used to display and summarize time to event data.

The planned sample size for analysis is at least 100 subjects which is believed to be adequate to provide an accurate characterization of EmboCube in a "real-world" clinical setting.

Analysis Population

- *Intention-to-Treat (ITT) Analysis Set:* includes all enrolled subjects.
- *Per-Protocol (PP) Analysis Set:* includes all enrolled subjects who met all inclusion/exclusion criteria with no major protocol deviations. This is a secondary analysis set for the primary safety and effectiveness endpoints, as well as secondary endpoints.

While ITT is intended as the primary analysis set for all safety and effectiveness endpoints, the primary safety and effectiveness endpoints will additionally be evaluated in the PP analysis sets as supportive information. All subjects excluded from ITT analysis set will be described.

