6 ANALYSIS POPULATION

The following analysis populations are identified for the study:

- Intention-to-Treat (ITT) analysis set: includes all enrolled subjects.
- Per-Protocol (PP) analysis set: includes all enrolled subjects who meet all inclusion/exclusion criteria with no major protocol deviations. This is a secondary analysis set for the primary safety and effectiveness endpoints, as well as secondary endpoints.

While the ITT analysis set is intended as the primary analysis set for all safety and effectiveness endpoints, the primary safety and effectiveness endpoints will also be evaluated in the PP analysis set as supportive information. All subjects excluded from the ITT analysis set will be described.

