8.3 SECONDARY DATA ANALYSES

All secondary endpoints will be tabulated. Means, SDs, and sample size will be used to summarize continuous variables. Distributions of continuous data will be examined and if non-normality is exhibited, medians and interquartile ranges will be presented. Frequencies and percentages will be used to summarize categorical variables. All available data will be used for each endpoint and no imputations will be performed.

Incidence of adverse events to 24 hours post-operative (serious and device- and/or procedure-related)

Endpoint Derivation:

- Serious adverse events as reported by the site, **AND**
- “Seriousness” is checked as anything other than “Not Serious”, **AND**
- Relationship to study device **AND/OR** relationship to study procedure is “Definitely related”

Incidence of adverse events between 24 hours and 28 days post-operative (serious and device- and/or procedure-related)

Endpoint Derivation:

- “Were there any serious and device- or procedure-related adverse events since the 24-hour contact visit?” is checked YES, **AND**
- Serious adverse events as reported by the site and in which “Seriousness” is checked as anything other than “Not Serious”, **AND**
- Relationship to study device **AND/OR** relationship to study procedure is “Definitely related”

Technical success defined as successful occlusion of the treated site as seen on post-embolization angiography

Endpoint Derivation:

- “Was occlusion of the treated area (as seen on post-embolization angiogram) successful?” is checked YES

Incidence of device observations related to EmboCube

Endpoint Derivation:

- “Was procedure aborted due to device observation?” is checked YES

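### Enrolment is conditional on receiving EmboCube, so a consented subject in whom use was attempted but no gelatin was delivered can fall outside ITT with no data

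*Protocol*

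**What the plan says.** Protocol 5.3 gives three rules that bear on who is enrolled.

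- Enrolment has conditions. Subjects who give written consent, "meet all eligibility criteria, and are treated with EmboCube Embolization Gelatin will be considered enrolled in the study".
- Non-receipt after prior consent is a screen failure: "Subjects who are consented prior to procedure but subsequently do not receive EmboCube Embolization Gelatin will be considered screen failures". The next sentence reads "These subjects will be entered on the screening log, but no data will be collected on screen failures".
- The section then ends with "Point of enrollment is the time of informed consent".

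The analysis set follows from enrolment. SAP 6 has "Intention-to-Treat (ITT) analysis set: includes all enrolled subjects", and Protocol 9 defines the set in the same way. Protocol 9 also promises that "All subjects excluded from ITT analysis set will be described", and SAP 6 repeats this.

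Two other places concern device problems. SAP 8.3 derives the device-observation endpoint from a single eCRF item, "Was procedure aborted due to device observation", answered yes. Protocol 7.4.3 requires every device observation, malfunction or failure to be notified to the Sponsor, and Protocol 11.2 repeats the timeline. Protocol 6.3 lists observations on handling and delivery among the procedural data.

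Neither document defines *treated* or *receive*, and neither mentions an attempt in which nothing was delivered.

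**The concern.** In a single-arm device study, the denominator should be fixed before the device has had a chance to succeed or fail. Here membership of ITT depends on receipt of the gelatin, which comes after the decision to use the device and which the device's own handling can determine. If preparation or delivery fails completely and the operator turns to another method, the plain wording makes that subject a screen failure.

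Such a case would then be missing from clinical success, technical success and device observations. Each omission moves the reported rate in the device's favour. The number of such cases may be small, but the study plans only about 100 subjects, and Protocol 1.5 says that its data will feed the risk analysis and the clinical evaluation report. With the terms undefined, up to 7 sites could also classify the same event differently, and could do so after seeing the outcome.

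**Working it through.** **1. Follow one subject through the text.** Take a subject who consented before the procedure, in whom EmboCube was prepared, delivery failed, and no gelatin entered the vessel.

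| Provision | Result for this subject |
|---|---|
| Protocol 5.3, enrolment conditions | Not treated, so not enrolled |
| Protocol 5.3, screen-failure rule | Screen failure, log entry only |
| Protocol 5.3, point of enrolment | Enrolled at consent |
| SAP 6, ITT | Out under the first two rows, in under the third |
| SAP 8.3, device observations | Should count if the procedure was aborted for a device observation, but the screen-failure rule leaves no data |
| Protocol 7.4.3 | The event is to be reported to the Sponsor; nothing places the subject in a denominator |

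If consent is sought only after the procedure, which Protocol 5.2 expects in many cases, the screen-failure sentence does not apply. The condition of being treated with EmboCube still excludes the subject.

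**2. The plan's own sample size.** Inputs from Protocol 9.4: p0 = 0.92, p = 0.90, margin 0.10, α = 0.05, power 80%, 15% loss. The implied threshold is 0.92 − 0.10 = 0.82. With one-sided α and the variance taken at p:

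n = (1.6449 + 0.8416)² × 0.90 × 0.10 / (0.90 − 0.82)² = 6.1826 × 0.09 / 0.0064 = 86.94, so 87.

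Allowing for loss, 87/0.85 = 102.4 (103), or 87 × 1.15 = 100.05. The stated 100 reproduces approximately, and this point does not challenge it.

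**3. Size under assumed counts.** Let k be the number of attempts with nothing delivered. The documents give no value for k. The 90/100 clinical successes and 98/100 technical successes are also assumptions. Each non-delivery is added back as a failure. SAP 8.1 specifies Clopper-Pearson limits: lower = Beta⁻¹(0.025; x, n − x + 1), upper = Beta⁻¹(0.975; x + 1, n − x), with x = 90 and n = 100 + k.

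| k | Clinical success | Exact 95% CI | Lower limit, exact 90% CI | Technical success 98/(100 + k) | Non-deliveries as device observations k/(100 + k) |
|---|---|---|---|---|---|
| 0 | 90.0% | 82.4% to 95.1% | 83.6% | 98.0% | 0.0% |
| 1 | 89.1% | 81.3% to 94.4% | 82.6% | 97.0% | 1.0% |
| 2 | 88.2% | 80.4% to 93.8% | 81.6% | 96.1% | 2.0% |
| 3 | 87.4% | 79.4% to 93.1% | 80.7% | 95.1% | 2.9% |
| 5 | 85.7% | 77.5% to 91.8% | 78.9% | 93.3% | 4.8% |

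Against 82%, the 95% lower limit crosses with one added failure. The 90% lower limit, which corresponds to one-sided 0.05, crosses with two.

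**The case against.** The strongest reply is that the screen-failure sentence was written for a different patient: one who consents beforehand and is then managed without EmboCube. That is a natural reading, and a treated-subject population is common in post-market follow-up. It stands to this extent: the text does not say that a failed attempt is a screen failure. That follows only from taking *receive* and *treated* at their plain meaning. But the text does not exclude the failed attempt either, and the point-of-enrolment sentence gives the opposite answer.

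Several stronger inferences are tempting, and the documents do not support them.

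- *Device failures are removed from ITT.* Protocol 12 defines a device failure as use according to the IFU without performance according to the IFU. Partial delivery, absent occlusion, rebleeding and malfunction after some gelatin is in place all occur in treated subjects, who stay in ITT. Only total non-delivery is at issue.
- *The device-observation endpoint is forced to zero.* A procedure can be aborted after some gelatin has been delivered, and the SAP item presumes eCRF data on at least some aborted procedures. Protocol 7.4.3 also gives a separate reporting route. The passages conflict; they do not show that all such events are lost.
- *Subjects excluded from ITT cannot be described.* The screening log in Protocol 5.1 and 5.3 allows at least a count, though little more.
- *The eligibility wording contradicts itself.* Protocol 5.3 reads coherently: subjects thought eligible are enrolled, and those found ineligible later remain with a deviation form.
- *Crossing 82% would change the study's conclusion.* Protocol 9 calls the analysis primarily descriptive, and neither Protocol 9.2 nor SAP 8.2 sets a success criterion. The 82% is only the sample-size threshold.

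**Conclusion.** The point holds in a limited form. Protocol 5.3 conditions enrolment on receipt of the device and bars data on pre-consented subjects who do not receive it, while also placing enrolment at consent. On the plain wording, a zero-delivery attempt leaves every ITT endpoint, and any such loss can only favour the device. The descriptive purpose does not remove the problem, because a descriptive rate still needs the right denominator.

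The effect is about 0.9 percentage points of clinical success for one case, 2.6 for three and 4.3 for five, starting from 90/100. These figures rest on the assumed counts and on treating each non-delivery as a failure. If there are no non-deliveries, nothing changes. The point is worth correcting because the correction is cheap and the rule is ambiguous; the documents do not show that the bias will be large.

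**What to change.** - **Protocol 5.3 and SAP 6:** define *treated* or *received* as any attempted delivery of EmboCube in a consented subject, whether or not gelatin was delivered. Examples are attempted introduction into the delivery catheter, or preparation that failed because of the device. Merely opening the pack is too wide a trigger, because it would count as failures subjects whose plan changed for reasons unrelated to the device. Reconcile the definition with the point-of-enrolment sentence.
- **ITT and SAP 8.2 and 8.3:** keep these subjects in ITT and state that a non-delivery counts as a technical failure, a clinical failure and a device observation. This must be explicit, because the occlusion item is not tied to EmboCube and could be answered yes after another embolic was used.
- **Data:** collect the existing eCRF data on them, subject to the consent rules in Protocol 5.2.
- **Screen failures:** reserve the term for subjects in whom no EmboCube use was attempted, or whose plan changed for reasons unrelated to the device. Report their number from the screening log.

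The cost is a short protocol and SAP wording change, a small eCRF adjustment, a note in site training, and ethics committee handling under Protocol 10.14. No additional procedures are needed. The reported rates may become slightly less favourable.
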